#### 12.2.2 Analysis for secondary outcome measures.

The focus of the study is to determine efficacy of ZNS for treatment of acute hearing loss based on the testing of hypothesis for primary outcome. In addition, we will also conduct analysis to evaluate other important audiologic measures. The secondary outcome measures are key audiological and clinical assessments of change in cochlear function and hearing loss: DPOAEs, ECochG, WIN testing. They will be measured as continuous level variables. We do not plan any adjustment of alpha error for multiple comparisons.

Analysis of variance (ANCOVA) will be used for comparison of outcome measures between each of the ZNS groups and placebo study group after controlling for baseline value and age, age, pre-op hearing dichotomized to normal to minimal hearing loss and slight to mild loss, noise exposure history dichotomized to high risk and low risk, exposure categorized as low (LAeq8hr < 80 dBA), moderate (LAeq8hr > 80 dBA but < 90 dBA), or high (LAeq8hr > 90 dBA).

Statistical analyses will be conducted using the SAS software (SAS Institute Inc., Cary, N.C., USA).

#### **Missing Data**

Every attempt will be made to ensure data completeness. We do not anticipate much loss to follow-up because of the relatively short time follow-up interval. Conservatively, we would estimate that fewer than 5% of subjects will drop out/withdraw from the study. The participant will be withdrawn from the study follow-up procedures if the participant withdraws consent, or the sponsor decides to close the study.

If any, the loss of data would almost certainly be due to the fact that the subjects refused to complete or did not show up for the assessment of PTS 30 days (+/- 3 days) after the surgery. If the participants reschedules the post-surgery appointment for a later date for any reason, and if this delay is within 30 days of the scheduled date, the data will be considered valid and used in the efficacy analysis. Any measure outside this time window of +30 days will be defined and considered missing data.

Missing PTS at 30 days will be imputed using SAS PROC MI procedure within each treatment group using the distribution implied by the non-missing data for the specific treatment group.

The SAS code below using MICE via the Fully Conditional Specification (FCS) statement will be used to impute the missing data under the missing at random (MAR) assumption.

```
PROC MI DATA=X SEED=<value> NIMPUTE=10 OUT=MI_OUT1 NOPRINT;
CLASS GROUP;
VAR AGE PTA LSurg......;
FCS LOGISTIC(PTS);
RUN;
```

The estimates of the analysis of the 10 imputed datasets will be then combined following Rubin's rules using PROC MIANALYZE procedure in SAS which will be of the form:

```
PROC MIANALYZE PARMS=GMPARMS COVB=GMCOVB PARMINFO=GMPINFO WCOV BCOV
TCOV; / *dataset "gmparms" contains the estimates and associated
standard errors for the mean parameters from each of the M=10 imputed
data sets.
dataset "gmcovb" contains the asymptotic covariance matrics
dataset "gmpinfo" contains parameter info*/
MODELEFFECTS group;
RUN:
```

#### 12.3 Sample Size Estimation

#### Sample size estimation for primary outcome measure.

The primary efficacy outcome will be the proportion of PTS positive subjects defined as the ratio of PTS-positive subjects to total number of subjects in each study arm/group. Using pilot data from a retrospective chart review of 75 similar patients undergoing ≥1-hour drill noise exposure, we estimate the proportion of PTS positive subjects in the placebo group will be 50%. We hypothesize that the expected effect of ZNS either pre-op or post-op will be a 50% reduction of the proportion of subjects with PTS positive as compared to placebo group. This is the desired clinically import effect for treating hearing loss for single dose of 100 mg ZNS.

The sample size for this study was calculated for the planned comparisons of each of the ZNS groups with the placebo group using a balanced design and a one-sided alpha level of 0.0125.

Based on the data from our retrospective study, using Fisher's exact test, we estimated that 78 subjects in the ZNS group and 78 subjects in the placebo group will be needed to provide us with 80.4 % power to detect a 50% reduction in the proportion of PTS positive subjects (from 50% to 25% corresponding to an

absolute proportion difference of 25%) at the 1-sided alpha level of 0.0125 for each ZNS-Placebo group comparison. Our one-sided hypothesis is supported by animal studies, and lack of any evidence of hearing loss as a side effect of ZNS in human studies. A total of 234 subjects will be enrolled to be randomized in this study. We will make all the needed effort to minimize and eliminate drop outs, and due to short term-follow-up of the study subjects in a period where they are under medical care, we do not expect any drop-outs or lost to follow-up.

All sample size calculations were carried out using PROC POWER procedure in SAS 9.4.

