#### 3.0 ELIGIBILITY CRITERIA

#### 3.1 Inclusion Criteria

- 1. Patients who are scheduled to undergo a skull-based surgery that requires at least 45 minutes of surgical-drilling.
- 2. At least 18 years of age.
- 3. Air conduction thresholds in the non-operated ears are to be no worse than 25 dB HL for pure tone average 0.5, 1, and 2 kHz with no individual threshold greater than 30 dB HL, and no worse than 45 dB HL at 4 kHz at screening.
- 4. Observed air-bone gap  $\leq$  10 dB HL at 0.5, 1, 2, and 4 kHz, with normal tympanometry.
- 5. Ability to understand and willingness to sign an IRB approved written informed consent document.

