2.7 Sample Size Determination for The Primary Efficacy Outcome Measure

The primary efficacy outcome will be the proportion of PTS positive subjects defined as the ratio of PTS-positive subjects to total number of subjects in each study arm/group. Using pilot data from a retrospective chart review of 75 similar patients undergoing \geq 1-hour drill noise exposure, we estimate the proportion of PTS positive subjects in the placebo group will be 50%. We hypothesize that the expected effect of ZNS either pre-op or post-op will be a 50% reduction of the proportion of subjects with PTS positive as compared to placebo group. This is the desired clinically significant effect for treating hearing loss for single dose of 100 mg ZNS.

The sample size for this study was calculated for the planned comparisons of each of the ZNS groups with the placebo group using a balanced design and a one-sided alpha level of 0.0125 Based on the data from our retrospective study, using Fisher's exact test we estimated that 78 subjects in the ZNS group and 78 subjects in the placebo group will be needed to provide us with 80.4 % power to detect a 50% reduction in the proportion of PTS positive subjects *(from 50% to*

^{**}Dispensed on the day of surgery with instruction to take first dose prior to surgery and second dose after surgery.

^{***} Plasma sample for PGx will be collected at baseline visit. Plasma sample for ZNS level and PGx, electrolyte panel, BUN, Cr, ALT, and AST will be collected 12 hours after first dose.

25% corresponding to an absolute proportion difference of 25%) at the 1-sided alpha level of 0.0125 for each ZNS-Placebo group comparison. A total of 234 subjects will be enrolled to be randomized in this study. All efforts will be made minimize and eliminate drop outs. Given the short term-follow-up of study subjects in a period where they are under medical care, few, if any, drop-outs or lost to follow-up are expected.

Sample size calculations were carried out using PROC POWER procedure in SAS 9.4.

3 Study Outcomes

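### The stated 80.4% power holds only with complete follow-up and a 50% placebo PTS rate; at the plan's own 5% loss ceiling it is about 78%

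*Protocol*

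**What the plan says.** **Sizing.** Protocol 12.3 and SAP 2.7 plan each ZNS-placebo comparison by Fisher's exact test at "a one-sided alpha level of 0.0125", with PTS falling from 50% to 25%. The Protocol states that "78 subjects in the ZNS group and 78 subjects in the placebo group will be needed to provide us with 80.4 % power", and SAP 2.7 gives the same figure. Enrolment is 234.

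**Loss to follow-up.** Protocol 12.3 says "we do not expect any drop-outs or lost to follow-up". SAP 2.7 is softer and expects little or no loss, without a figure. The Missing Data text in Protocol 12.2.2 says that, conservatively, "we would estimate that fewer than 5% of subjects will drop out/withdraw from the study"; SAP 5.2 repeats this. Both plan multiple imputation of missing PTS within each arm under MAR. The timeline paragraph in Protocol 12.4 also allows for attrition.

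**Placebo rate.** The 50% was obtained "Using pilot data from a retrospective chart review of 75 similar patients undergoing" at least 1 hour of drill noise. Protocol 3.1 admits patients having "skull-based surgery that requires at least 45 minutes of surgical-drilling". Protocol 12.4 and SAP 4.4 still describe 45 minutes as an option to explore if accrual is poor.

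**The concern.** The sample size section and the missing-data section of the same protocol start from different expectations of loss, and only the more favourable one enters the power. The margin over 80% is 0.4 points, so a small loss uses it up.

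The placebo rate raises a separate question. Protocol 1.2 says that longer noise exposure is more hazardous, which on the plan's own reasoning points to less PTS with shorter drilling. Protocol 12.4 counts about 50 patients a year with 1 hour or more of drilling. Over 4 years that is about 200, fewer than 234, so without added sites some patients with shorter drilling would be needed.

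Readers of a null result will use 80.4% to judge what the trial could have detected. They should be able to see what it is conditional on.

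**Working it through.** **Inputs** (Protocol 12.3, SAP 2.7): placebo p1 = 0.50, ZNS p2 = 0.25, n = 78 per arm, one-sided alpha = 0.0125, Fisher's exact test.

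**Step 1: reproduce 80.4%.** The continuity-corrected arcsine approximation is

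power = Φ{[asin√(p1 − 1/2n) − asin√(p2 + 1/2n)]·√(2n) − z(1−alpha)}.

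With n = 78, 1/2n = 0.0064, √156 = 12.49 and z(0.9875) = 2.241:

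(0.7790 − 0.5310) × 12.49 − 2.241 ≈ 0.856, and Φ(0.856) = 80.4%.

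Full enumeration sums the two binomial probabilities over every table whose one-sided hypergeometric p-value is at most 0.0125. It gives 80.7%. The stated figure is reproduced.

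**Step 2: allowance for loss.** 3 x 78 = 234, so there is none.

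**Step 3: power after loss.** The ceiling is 78 × 0.95 = 74.1, so 74 per arm.

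| Evaluable per arm | Exact Fisher | Arcsine approximation |
|---|---|---|
| 78 | 80.7% | 80.4% |
| 77 | 80.1% | 79.8% |
| 76 | 79.2% | 79.2% |
| 75 | 78.3% | 78.5% |
| 74 | 77.9% | 77.8% |

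The largest fall is 80.7 − 77.9 = 2.8 points (exact) or 80.4 − 77.8 = 2.6 points (approximation). If every arm stays strictly under 5%, at most 3 of 78 are lost (3.8%), which is the 75 row.

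Imputation does not restore the 78 row. Missing values are drawn from the distribution of the same arm's observed values, so they carry little new information about that arm's rate.

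**Step 4: the placebo rate.** No document gives a PTS rate for 45 to 60 minutes of drilling, or the share of such patients, so the rates below are assumptions. Exact Fisher power:

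| Placebo rate (assumed) | Halved, 78 per arm | Halved, 74 per arm | 25-point difference held, 78 per arm |
|---|---|---|---|
| 55% | 88.0% | 84.9% | 79.9% |
| 50% (plan) | 80.7% | 77.9% | 80.7% |
| 45% | 72.2% | 70.1% | 83.4% |
| 40% | 63.1% | 60.9% | 87.7% |

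Power moves in opposite directions on the two effect scales.

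**Step 5: precision of the pilot rate.** The pilot count is not given. If 37 or 38 of 75 were positive, the 95% Wilson intervals are 38.3% to 60.4% and 39.6% to 61.7%, so roughly 38% to 62%.

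All figures are per comparison and before the futility look, which can only lower power.

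**The case against.** The strongest defence is that 80.4% is a conditional statement whose conditions are printed beside it. That stands: the figure is not a calculation error. A reader might infer that the design lacks the power it states, but the documents do not support that reading. With 78 followed per arm and 50% against 25%, it has that power.

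The loss is also bounded. Fewer than 5% is a ceiling that the plan calls conservative, not an expected loss. Audiograms up to 30 days late still count, which limits missing data. By exact calculation, one lost per arm leaves 80.1%. This limits the size of the point but does not reconcile the two statements.

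Protocol 12.4 and SAP 9 already report 79.6% overall power. That figure covers the futility look and success on one or both comparisons. It does not address loss to follow-up.

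A reader might also infer that admitting patients from 45 minutes cuts power to the low 70s or 60s. That does not follow. Forty-five minutes is a minimum, and the enrolled distribution is unknown. The fall appears only if the rate drops and ZNS still halves it. Protocol 12.3 does state the effect as a halving, but it also gives the 25-point difference, and SAP 3.2.1 and 3.2.2 word the hypotheses on that absolute scale. On that scale power rises. The pilot interval also reaches above 50%.

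**Conclusion.** The point holds in a limited form. The statements on loss conflict, and the sample size carries no allowance. At the plan's own ceiling, per-comparison power is about 78% rather than 80.4%, a fall of 2.6 to 2.8 points, and it is under 80% once two per arm are lost. This assumes 50% against 25%, equal loss in the two arms compared, and little recovery from within-arm imputation.

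The mismatch between the pilot's drilling time and the eligibility criterion is plain in the text. Its effect on power is not established in size or direction, so it calls for disclosure and a sensitivity range, not a claim of lost power.

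**What to change.** 1. In Protocol 12.3, replace the statement that no loss is expected with the fewer-than-5% figure from Protocol 12.2.2. In SAP 2.7, align the looser wording with the same figure.
2. In both sections, state that per-comparison power is 80.4% with complete follow-up and about 78% at the 5% ceiling (74 evaluable per arm), before the futility look.
3. In both, state that the 50% rate comes from patients with at least 1 hour of drilling, while eligibility starts at 45 minutes. Reconcile Protocol 12.4 and SAP 4.4, which still treat 45 minutes as a fallback, with Protocol 3.1.
4. Add a two-sided sensitivity range, labelled as assumption, at 78 per arm. With halving: 88% at a 55% placebo rate, 72% at 45%, 63% at 40%. With the 25-point difference held: 83% at 45%, 88% at 40%.

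The cost is wording only, and the stated power becomes slightly less favourable. If the sponsor prefers to keep 78 evaluable per arm at 5% loss, 78/0.95 = 82.1, so 83 per arm and 249 in total, which is 15 more participants.

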## 12.4 Interim Analysis

A sponsor blinded interim analysis focused on the primary endpoint after 33% of the patients have completed participation in the study (26 in each group). The independent programmer will prepare the datasets for each pairwise comparison (subsets of data) using a pre-prepared SAS code and will freeze them for the interim analysis. To ensure the double blinding of the study the subjects will not be presented in the assigned groups. The blinded statistician will estimate the overall proportion of PTS positive subjects in each group.

For each pair-wise comparison, with 33% information, the trial would be stopped for futility if the interim z-value  $\leq 0.6850$  (p=0.49 2-sided) for either or both comparisons, corresponding to a conditional power of  $\leq 10\%$  for each comparison. This design would provide 79.6% overall power (i.e. the probability of passing futility and reaching p<0.0125 for one or both comparisons in the final analysis would be 79.6%).

Based on interim analysis the following actions may be taken:

- Stop only one of the ZNS groups for futility
- Stop the trial (both ZNS groups) for futility
- Continue the trial as planned.

Early stopping rules related to serious adverse events: In the event of a serious adverse event, DSMB will evaluate the association of the serious adverse events with the study arm, break the blind if needed, and if found to be associated with treatment, DSMB will consider the study for revision or stopping.

Serious feasibility or design difficulties: If one year after the start of the trial, <50% of the planned accrual goals are met, DSM and the study team will discuss difficulties in recruitment. Patient remuneration will be revised, if needed. If there are not enough patients meeting inclusion/exclusion criteria, then the criteria will be revised without impacting study objectives. If there are not enough patients that undergo more than 1-hr drilling time during surgery, we will explore

including into the study, patients with drilling time at least 45 minutes, expanding audiometric criteria, or expanding to different institutions.

The overall timing associated with the study is based on our previous clinical study experience. Approximately 50 patients per year receive skull surgery that requires 1 hour or more of drilling time at WUSM. Accounting for participant attrition, we plan to finish the study within 4 years. If participant enrollment numbers are consistently below expectations as determined by the study team and DSMC, plans will be made to add additional sites or adjust study inclusion criteria (e.g. including head/skull surgeries requiring less than 1 hour of drilling time).

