9 INTERIM ANALYSIS

A sponsor blinded interim analysis focused on the primary endpoint after 33% of the patients have completed participation in the study (26 in each group). The independent programmer will prepare the datasets for each pairwise comparison (subsets of data) using a pre-prepared SAS code and will freeze them for the interim analysis. To ensure the double blinding of the study the subjects will not be presented in the assigned groups. The blinded statistician will estimate the overall proportion of PTS positive subjects in each group. Then one-sided Fisher's exact test will be used to compare the proportion of subjects with PTS positive in ZNS group with the proportion of patients with PTS positive in the placebo group. one-sided p-value (p_i) from Fisher's Exact Test will be converted to a z-value using the inverse Normal transformation [1,2], i.e. $z_i = \Phi^{-1}(1 - p_i)$, where $\Phi^{-1}(\cdot)$ represents the inverse standard Normal cumulative distribution function.

For each pair-wise comparison, with 33% information, the trial would be stopped for futility if the interim z-value ≤ 0.6850 for either or both comparisons, corresponding to a conditional power of $\leq 10\%$ for each comparison. This design would provide 79.6% overall power (i.e. the probability of passing futility and reaching p ≤ 0.0125 for one or both comparisons in the final analysis would be 79.6%).

Based on interim analysis the following actions may be taken:

- Stop only one of the ZNS groups for futility
- Stop the trial (both ZNS groups) for futility
- Continue the trial as planned.

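### The futility sentence stops the whole trial when either comparison is futile, but the action list below it treats stopping one ZNS arm as a separate decision; the plan must say which applies

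*Protocol*

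**What the plan says.** Protocol 12.4 and SAP 9 plan one interim look at the primary endpoint, "after 33% of the patients have completed participation in the study (26 in each group"). The criterion in both is that "the trial would be stopped for futility if the interim z-value" is no greater than 0.6850 "for either or both comparisons, corresponding to a conditional power of" at most 10%. The Protocol adds that this z corresponds to a two-sided p of 0.49.

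The list of possible actions that follows, also in both documents, has three items. Two concern stopping: "Stop only one of the ZNS groups for futility" and, separately, "Stop the trial (both ZNS groups) for futility". The third is to continue. The list is introduced as actions that may be taken. No sentence says which pattern of z-values leads to which action.

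Only the SAP says how z is obtained: "Then one-sided Fisher's exact test will be used to compare the proportion of subjects with PTS positive in ZNS group" with placebo, and the one-sided p-value is converted to z by the inverse normal. Both documents state an overall power of 79.6%, defined as passing futility and reaching significance in one or both comparisons.

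**The concern.** Suppose one ZNS arm is at or below the boundary and the other is above it. The criterion sentence closes all three arms. The action list allows the second ZNS arm and placebo to continue. Two boards, each following the text in good faith, could decide differently on the same data, and a closure cannot be undone.

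The sentence as written also fits poorly with the design. The primary objective covers preoperative and/or postoperative ZNS. SAP 2.3 has placebo serve as a shared control against which each active group is compared independently. Each comparison has its own hypotheses and its own one-sided 0.0125. Futility of one timing is therefore no reason to abandon the other.

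**Working it through.** **Inputs.** Final size "78 subjects in the ZNS group and 78 subjects in the placebo group", hence 234 in three arms; interim size 26 per arm; placebo 50% and effective arm 25%; one-sided alpha 0.0125 per comparison (Protocol 12.3); boundary z ≤ 0.6850 (Protocol 12.4, SAP 9). The documents give no rate for an ineffective or weaker ZNS arm. I assume 50% (null) and 37.5% (half the effect) and show both.

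**Reproducing the plan's figures.**

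- *Power per comparison.* The continuity-corrected arcsine approximation to Fisher's test is Φ(2[arcsin√(p₁ − 1/2n) − arcsin√(p₂ + 1/2n)] / √(2/n) − z₀.₉₈₇₅). With n = 78, p₁ = 0.50 and p₂ = 0.25 it is Φ(2[0.7790 − 0.5310]/0.1601 − 2.2414) = Φ(0.856) = 80.4%, the stated figure. Exact enumeration gives 80.7%.
- *Boundary.* Conditional power under the current trend at t = 1/3 is Φ((z/√t − z₀.₉₈₇₅)/√(1 − t)) = Φ((1.186 − 2.241)/0.816) = Φ(−1.292) = 9.8%. The two-sided p for z = 0.685 is 0.493. Both agree with the text.

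**Comparing the two readings.** I simulated one million three-arm trials with a shared placebo group. Interim z comes from the one-sided Fisher p at 26 per arm, as in SAP 9. A comparison is significant if the final one-sided Fisher p is ≤ 0.0125 at 78 per arm. The first ZNS arm is at 25% throughout. In the last two columns the first figure is arm by arm and the second is the sentence as written.

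| Second ZNS arm | Either futile | Both futile | First arm shown | At least one shown |
|---|---|---|---|---|
| 25% (plan's hypothesis) | 29% | 8% | 71% v 63% | 85% v 68% |
| 37.5% (assumed) | 56% | 15% | 71% v 40% | 72% v 40% |
| 50% (assumed) | 84% | 18% | 71% v 15% | 71% v 15% |

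The whole trial stops with the both-futile frequency under arm-by-arm stopping, and with the either-futile frequency under the sentence as written.

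A simple bound confirms the last row. Under the sentence as written, nothing can be shown unless both arms pass, and both pass in 100 − 83.9 = 16.1% of trials. The 15% must lie below that.

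With a null second arm, the effective arm passes its own look but is closed because of the other in 65.3% of all trials. It passes in 100 − 18.6 = 81.4%, so this is 65.3/81.4 = 80% of the trials in which it passed. With a half-effective second arm the corresponding figure is 37.1/81.4 = 46%.

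**Sensitivity to the definition of z.** Section 12.4 of the Protocol does not define z. With a pooled z at the interim, the null-second-arm contrast is 75% v 22%, the half-effective contrast is 75% v 49%, and the chance of at least one significant comparison with both arms at 25% is 88% v 77%.

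**Does the stated 79.6% show which rule was meant?** I used a normal model with a shared control and both arms at the planned effect:

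| Power per comparison | At least one shown, arm by arm | At least one shown, as written | Single comparison |
|---|---|---|---|
| 80.4% (as stated) | 87.6% | 74.2% | 74.1% |
| 84.6% (uncorrected z-test) | 90.6% | 78.2% | 78.5% |

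Nothing in the first row is within two points of 79.6%. In the second row, the as-written rule and the single comparison are. Arm-by-arm stopping is not close in either row.

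**The case against.** The strongest reply is that the sentence should not be read alone. It opens by referring to each pairwise comparison and closes with conditional power for each comparison. The list equates stopping the trial with stopping both ZNS groups. If one futile comparison closed everything, the first listed action could never be used. Read together, either points to one group and both points to the trial. I accept this as the likely intent. It does not remove the conflict, because the sentence that carries the criterion still names the trial, and the list supplies no criterion of its own.

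The size also depends on the scenario. The plan hypothesises 25% in each ZNS arm, and there the loss is from 85% to 68%. The fall to 15% needs both the sentence applied as written and an assumed null arm.

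Two stronger readings are tempting. A reader might infer that one weak arm would usually end the trial of an effective one. That holds for a null second arm (80% of trials in which the effective arm passed) but not for a half-effective one (46%). A reader might also infer from the and/or objective that success of only one timing is the most likely result. The objective states what is tested and says nothing about which outcome is likely.

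Finally, the actions are permissive, so a board could use its discretion to avoid the harm. That is possible, but the text then does not say how far the discretion goes.

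**Conclusion.** The contradiction is real, stands in the current text of both documents, and is not resolved elsewhere in either. It is a wording conflict in a stopping rule, and the loss arises only if the criterion sentence is applied as written. In that case the chance of at least one significant comparison falls from about 85% to 68% on the plan's own assumptions. The chance of showing an effective arm falls from 71% to 40% if the other is assumed half-effective, and from 71% to 15% if it is assumed null (75% to 22% with a pooled z).

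The documents do not support the conclusion that the sponsor intended trial-wide stopping; the action list points the other way. Nor does the 79.6% settle the matter, since it matches no reading when derived from the stated 80.4% per comparison. It does need recomputing, because under arm-by-arm stopping it does not describe the design.

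**What to change.** In Protocol 12.4 and SAP 9, before the interim look, replace the criterion sentence with wording such as:

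> *The futility boundary is applied to each ZNS–placebo comparison separately. A ZNS group whose interim z-value is ≤ 0.6850 meets the criterion for stopping that group, and the other ZNS group and placebo continue. The trial meets the criterion for stopping only if both comparisons are ≤ 0.6850.*

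Then:

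1. State whether the boundary is binding or leaves the DSMB discretion, so that it agrees with the permissive wording of the action list.
2. Recompute the 79.6% under this rule and give the method. Simulation with exact Fisher p-values gives about 85% for at least one significant comparison with both arms at 25%.
3. Put the SAP's definition of the interim z in the Protocol as well.

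The cost is a short text change in each document and one recalculation. It needs no more patients and leaves the boundary and final test unchanged. Each comparison is still tested at one-sided 0.0125, so the Bonferroni control is unaffected. The timing matters: choosing between the readings after the interim z-values are known would make the rule data-driven.

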#### Primary analysis.

Frequency and relative frequency will be used to describe the distribution of the primary outcome measure in each study group. To assess efficacy, Fisher's exact test will be used to compare the proportion of subjects with PTS positive in ZNS group with the proportion of patients with PTS positive in the placebo group.

To provide an estimate of treatment effect a supportive logistic regression analysis will be done with covariates: age, pre-op hearing dichotomized to normal to minimal hearing loss and slight to mild loss, noise exposure history dichotomized to high risk and low risk, exposure categorized as low (8-hour equivalent A-weighted sound level in decibel (LAeq8hr) < 80 dBA), moderate (LAeq8hr > 80 dBA but < 90 dBA), or high (LAeq8hr > 90 dBA).

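### The 79.6% overall power does not follow from the planned Fisher tests, and the futility look cuts per-comparison power from about 80% to about 71% without either document saying so

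*Protocol*

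**What the plan says.** Protocol 12.3 sizes the trial for each ZNS–placebo comparison: 78 per arm "will be needed to provide us with 80.4 % power" at one-sided alpha 0.0125, with PTS rates of 50% on placebo and 25% on ZNS. SAP 2.7 repeats this: "will be needed to provide us with 80.4 % power to detect a 50% reduction". The final test is Fisher's: "exact test will be used to compare the proportion of subjects with PTS positive in ZNS group" with that in placebo (Protocol 12.2.1).

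Protocol 12.4 and SAP 9 add an interim look at 26 per arm. Under both, "the trial would be stopped for futility if the interim z-value" is at or below 0.6850 in either or both comparisons. This is said to correspond to conditional power of 10% or less. SAP 9 defines the z: the one-sided p from Fisher's Exact "Test will be converted to a z-value using the inverse Normal transformation". Both sections then give a single operating characteristic: "This design would provide 79.6% overall power (i.e. the probability of passing futility and reaching p<0.0125 for one or both comparisons". The Protocol ends with "Based on interim analysis the following actions may be taken", and the first action is "Stop only one of the ZNS groups for futility". The others are to stop both ZNS groups or to continue.

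**The concern.** A reader who sees 80.4% in the sample-size section and 79.6% in the interim section will conclude that the futility look costs less than one point of power. The two figures do not measure the same thing. The first is for one comparison with no look. The second is for success in at least one of two comparisons, with the look.

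The boundary is also demanding for 26 per arm, because Fisher's p is conservative at that size. If the rule stops effective arms often, the trial falls below the 80% per comparison it was sized for, and the sponsor and DSMB would be judging the look on a figure that does not describe it.

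The rule itself can be read in two ways. The sentence says the trial stops if either comparison is futile, while the action list allows one arm to stop alone.

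**Working it through.** **Inputs.** One-sided alpha 0.0125, 50% v 25%, and 78 per arm (Protocol 12.3, SAP 2.7). A common placebo arm (SAP 2.3). Interim at 26 per arm with futility at z ≤ 0.6850 (Protocol 12.4, SAP 9). z = Φ⁻¹(1 − p) from a one-sided Fisher p (SAP 9). Final Fisher test (Protocol 12.2.1). No missing outcomes, as in Protocol 12.3.

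**The plan's figures that reproduce.**
- Fixed-sample Fisher power at 78 v 78: 80.41% by the Walters arcsine approximation and 80.74% by exact enumeration. The stated 80.4% is correct without a look.
- Conditional power at z = 0.685, t = 1/3, critical value 2.2414, under the interim trend: B = 0.685 × √(1/3) = 0.3955 and drift = 0.685 / √(1/3) = 1.1865. Then Φ[(0.3955 + 1.1865 × 2/3 − 2.2414) / √(2/3)] = Φ(−1.292) = 9.8%. The stated 10% or less is correct on that basis, which the text does not name. Under the design effect (drift 3.0974, set from 80.4%) it is about 61%.

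**The interim rule in counts.** z ≤ 0.6850 means a one-sided Fisher p of at least 1 − Φ(0.685) = 0.2467. With 13/26 PTS on placebo, 9/26 on ZNS gives z = 0.841 (continue) and 10/26 gives z = 0.558 (stop).

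**Exact enumeration.** Binomial counts were enumerated at both stages, conditioning on the shared placebo counts. An arm succeeds if interim z > 0.6850 and final Fisher p ≤ 0.0125.

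| Quantity (rule followed) | Result |
|---|---|
| Effective arm stopped at the interim | 18.6% |
| Power per comparison, no look | 80.7% |
| Power per comparison, with look | 71.1% |
| Both arms effective, both succeed, arms stop singly | 57.4% |
| Both effective, at least one succeeds, arms stop singly | 84.9% |
| Both effective, at least one succeeds, either low z stops the trial | 68.3% |
| One effective, at least one succeeds, arms stop singly | 71.1% (71.15%) |
| One effective, at least one succeeds, either low z stops the trial | 14.9% |

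Check on the 84.9%: 2 × 0.7113 − 0.5742 = 0.8484 (0.8485 before rounding). The loss per comparison is 80.7 − 71.1 = 9.6 points. A simulation of 1,000,000 trials agrees (71.1% and 84.8%).

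**How often the two stopping readings differ.** They differ when exactly one comparison is futile. With both arms effective, both are futile in 8.46% of trials, so exactly one is futile in 2 × 18.59 − 2 × 8.46 = 20.3%. With one arm effective, the figure is 65.7%.

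**Where 79.6% might come from.** No calculation with the planned tests gives it. Those that come near are off-plan:
- uncorrected z-tests at both looks: 78.9% per comparison (79.1% unpooled), or 78.2% for at least one success with whole-trial stopping;
- normal theory with unpooled variance: 80.5% per comparison;
- Fisher with 0.0125 read as two-sided: 80.6% for at least one success.

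A single-comparison normal approximation given the wrong label is a plausible source, but that is inference.

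**The case against.** The strongest reply has four parts.

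- **79.6% is conservative on its own definition**, since the planned tests give 84.9%. That is true only if both arms work and are stopped singly. If one arm works the figure is 71.1%, and under whole-trial stopping with both effective it is 68.3%.
- **80.4% is labelled as a fixed-sample Fisher figure and is correct.** This stands: the fault is an omission. It still matters, because 80.4% followed by 79.6% hides a loss of 9.6 points per comparison.
- **The 71% depends on the Fisher-to-z conversion, which only SAP 9 defines.** The dependence is real. An uncorrected z at the interim with a Fisher final test gives 75.4%, so about 5.3 points come from the look itself and 4.3 from the conversion. SAP 9 does define the statistic, however, and either reading is below 80%.
- **The stopping sentence opens by referring to each pairwise comparison, so the action list settles its meaning.** Single-arm stopping is indeed the more natural intent. The sentence nevertheless says the trial stops if either comparison is futile, and a DSMB should not have to infer the rule.

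The actions are also worded as permissive. The stated 79.6% is itself conditional on passing futility, so the comparison here is like for like, but the plan should say whether the rule binds.

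**Conclusion.** The concern holds. The 79.6% is wrong as defined: the planned tests give about 85% for at least one success when both arms work and are stopped singly, and about 71% when only one works. The look lowers power for each comparison from 80.7% exact (80.4% stated) to 71.1%, and neither document discloses this. The stopping sentence and the action list conflict, and the conflict matters in 20% of trials if both arms work and 66% if one does.

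These results assume rates of 50% v 25%, complete data, the SAP 9 interim statistic, and a rule that is followed. Type I error is not inflated. The 10% conditional power is correct under the interim trend. The correction should be made before the interim analysis, when the rule is applied.

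**What to change.** 1. In Protocol 12.4 and SAP 9, replace the 79.6% sentence with: *If the futility rule is followed, power is about 71% per comparison, and about 85% for at least one success when both ZNS arms work (71% when one works).* The 85% presupposes item 3. Add the SAP 9 definition of z to Protocol 12.4 so that the figures can be reproduced there.
2. In Protocol 12.3 and SAP 2.7, state that 80.4% is power before the futility look.
3. State the rule per comparison: a ZNS arm is futile if its own z ≤ 0.6850, and the whole trial stops only if both comparisons are futile. If the sponsor intends whole-trial stopping on either comparison, the action list must change and the figure for both arms effective is 68.3%.
4. State whether the rule is binding, and that the 10% conditional power is under the interim trend.

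The cost is wording and restated figures, with no extra patients and no change to tests or alpha. The stated per-comparison power becomes less favourable (71% rather than 80.4%).

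Optional, for the sponsor to weigh: an uncorrected score z at the interim would raise power to 75.4% per comparison and 88.0% for at least one success with both arms effective. It would stop an ineffective arm (50% v 50%) 75.6% of the time rather than 83.4%.
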